Aim 3. To explore the preliminary effectiveness of the pilot reintegration intervention. Within the pilot intervention study, we will explore preliminary effectiveness of the intervention on increases in our primary outcome of reintegration score and secondary outcomes of quality of life and depression through 1) comparison of baseline to six-month scores among intervention participants; and 2) comparison of six-month reintegration, quality of life, and depression scores to six-month data from a different study among women who participated in a longitudinal cohort study of recovery and reintegration in the year following fistula repair.

This proposed research is a first step in moving forward robust strategies for optimizing women's health and quality of life following fistula repair, providing important information on feasibility and acceptability of a multi-component intervention to improve women's physical and psychosocial quality of life in conjunction with fistula surgery within a referral hospital context.

The results from the pilot study will be used to understand and improve feasibility and acceptability of the intervention package, and will inform the development of a subsequent project to test the effectiveness of the intervention among a robust sample size. Data from this study will be an important component of that next proposal.

CENTRAL STUDY HYPOTHESIS. Our central study hypothesis is that the provision of reintegration assistance to women repaired for genital fistula incorporating health education, physiotherapy training, psychosocial counselling and economic empowerment will be feasible and acceptable to intervention recipients and stakeholders.

BACKGROUND AND JUSTIFICATION

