We propose concurrently targeting four specific areas to improve the lives of women that have suffered from fistula including health education, physical rehabilitation, psychosocial therapy, and economic empowerment. Informed by theoretical frameworks adopted from the interdisciplinary fields of health behavior, women's empowerment, and implementation science and the developing evidence base previously discussed, addressing each of these areas will assist women in overcoming the mental and physical disabilities that they may have suffered as a result of the fistula (physical rehabilitation and psychological therapy), ensure they are appropriately educated about fistula and reproductive health for optimizing recovery and enhancing post-repair health (health education) and address their economic needs to improve quality of life and prevent fistula recurrence in subsequent delivery by achieving the status and financial standing to access timely obstetric care (economic empowerment). In addition, certain components of our anticipated intervention will be directly targeted to women's partners or close family members, who are important sources of social support and critical links between afflicted women and their communities. This will be the first rigorously designed and evaluated multi-component intervention to address all these theoretically important supports for female genital fistula reintegration to our knowledge.

Figure 1. Conceptual Framework Informing Intervention Needs of Women with Genital Fistula

APPROACH

OVERVIEW OF STUDY DESIGN

Given the pilot nature of the current project and our primary objective to understand intervention feasibility and acceptability outcomes, we propose a quasi-experimental design for the current study. The study is being done to inform the subsequent development of a cluster-randomized controlled trial to estimate impact on effectiveness; however, no randomization will be undertaken at this stage of the research, and all women enrolled in the study will participate in the intervention. Assessment of preliminary effectiveness (Aim 3) in the current pilot study is exploratory, and will include change over time from pre-surgery as well as comparison with existing data from similar women that was collected within the context of a different research study.

STUDY SETTING

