Our research program seeks to improve physical and psychosocial outcomes of women undergoing surgery for female genital fistula in Uganda. The data collection activities for the pilot test of the intervention will be based at two hospitals in Kampala, Uganda: Mulago Specialized Women and Neonatal Hospital and Kawempe National Referral Hospital, as fistula repair surgeries are conducted at both of these locations by the same team. These facilities were selected based on volume of fistula repair and prior clinical and research collaboration. They provide fistula repair as an ongoing urogynecological service, supplemented by several annual fistula repair camps. Surgeons are International Federation of Gynecologists and Obstetricians (FIGO) certified fistula surgical trainers who routinely supervise trainees country-wide. From 2010 through 2015, an average of 190 women per year underwent genital fistula surgery at Mulago Hospital.⁴⁹

In this setting, the current standard of care for women accessing fistula surgery includes some unstructured health education and counseling on post-repair behaviors, and women are instructed on kegel exercises for pelvic floor strengthening. Women with significant needs are referred. However, these adjunct services are not offered as a structured program and referral is only made for the most severe cases, leaving women who might benefit from some psychological and physiotherapy services without.

STUDY PARTICIPANTS

Study participants will include 30 women who receive surgical care for female genital fistula at Mulago and Kawempe Hospitals in Kampala, Uganda. Women are referred to these services from providers at Mulago/Kawempe, nearby clinics or hospitals, or learn about the services from friends, relatives, and radio advertisements. Women will be considered eligible for participation after undergoing fistula surgery, if they are above age 18 or considered emancipated minors under Ugandan law, and if they are able to provide consent for the study. Up to 15 of the intervention recipients will be invited for subsequent in-depth interview for a more nuanced understanding of their experience participating in the intervention and its impact; they will be purposively selected with variability in the range of outcomes observed in the quantitative data collection: reintegration score, depression/anxiety, and economic status. This sample size has been selected for feasibility.

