Acceptability assessment (Aim 2) will incorporate interviews with up to 10 key stakeholders including facility staff implementing the intervention (n=3-5), providers working in fistula care at the facility, who will have spoken with women receiving the intervention but who have not directly delivered the intervention, (n=2-4) and hospital administrators *who may have important insight on implementation of the intervention outside of a research context and its sustainability* (n=1-2). This sample size has been selected for feasibility.

One of our exploratory comparisons for preliminary effectiveness (Aim 3) will be among the same participants (pre-post); however, the other comparison will be with existing data collected during a longitudinal cohort study we conducted among 60 women undergoing fistula care at Mulago Hospital in 2015-2016 and followed for a 1-year period.^{11,14}

RECRUITMENT AND ENROLLMENT

Intervention recipients: Potential intervention recipients will be recruited for participation in the study at the fistula ward at Mulago/Kawempe. Given current and historical rates of women's presentation for fistula care, we plan to recruit all women who present for care who meet our eligibility criteria. Our research staff will identify which women meet the eligibility criteria of the study based on personal knowledge, review of surgical logbooks and through discussion with other fistula ward personnel. Women will be approached for recruitment when identified as eligible, potentially several days prior to surgery. Study staff will describe the study goals and procedures, ensuring women's understanding of the study procedures and risks, and ascertain women's interest in participating through the informed consent process. Women who are interested in participating will be requested to provide written confirmation of consent through signature or thumbprint (with witness).

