Quantitative data. Data from surveys will be entered into a password-protected database. Confidentiality will be protected by secure data handling. Data quality practices will include range and logical checks built into data entry, double entry, and error checks. We will examine overall status at each time point for each variable, investigate patterns and types of missing data and non-response, and inspect distributions of mediating and outcome variables to identify outlying or unusual values and assess distributional characteristics. Data analysis: We will describe respondent characteristics and primary outcomes (Aims 1&2 - acceptability and feasibility; section a in Table 2) using frequency tables and descriptive statistics (e.g. means, standard deviations, medians, inter-quartile ranges, and proportions). Preliminary effectiveness (Aim 3) will be conducted by bivariate comparisons of pre vs. post assessments (within our main sample) of reintegration score (primary), quality of life and depression (secondary) and comparison between our external control group using similar data from the same time since surgery using the appropriate distributional tests (paired sample t-test and Stuart-Maxwell tests for pre-post comparison, and two sample t-test and chi-square test for external comparison).

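### The exploratory six-month comparison with the 2015-2016 Mulago cohort is crude: no balance table and no adjusted estimate for measured case mix

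*Combined protocol and SAP*

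**What the plan says.** Aim 3 in the Specific Aims includes a "comparison of six-month reintegration, quality of life, and depression scores to six-month data from a different study". The Study Participants section identifies that source as "existing data collected during a longitudinal cohort study we conducted among 60 women undergoing fistula care at Mulago Hospital in 2015-2016". The Data Analysis Plans section (Quantitative data) is the only place that states the method. It describes a "comparison between our external control group using similar data from the same time since surgery" and names the "two sample t-test and chi-square test for external comparison".

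The Overview of Study Design sets the standing of this work: "Assessment of preliminary effectiveness (Aim 3) in the current pilot study is exploratory". It describes the approach as "change over time from pre-surgery as well as comparison with existing data from similar women". The following step is also stated there: "The study is being done to inform the subsequent development of a cluster-randomized controlled trial to estimate impact on effectiveness".

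Some features are aligned. Time since surgery is the same in both series. The cohort was treated at Mulago, one of the two current sites, and the Study Setting section says that "fistula repair surgeries are conducted at both of these locations by the same team".

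No section plans covariates, matching, weighting, stratification or a table of pilot against cohort baseline characteristics. The analysis section does promise to describe respondent characteristics, but does not extend this to the cohort.

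**The concern.** The two series were not randomised against each other and were enrolled about five years apart. The cohort dates from 2015-2016, and the Timeline text hopes to begin recruitment in December 2020. A two-sample test on raw six-month scores estimates the intervention effect plus any difference in prognosis between the women enrolled, and cannot separate the two. The similarity of the women is asserted, and no planned analysis examines it.

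The protocol's own figures suggest that prognosis matters. The Background section gives repair success at Mulago as 50% to 90% depending on severity. The Study Goals and Objectives section reports reintegration scores 21.9 points lower in women with persistent symptoms at twelve months.

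At stake is the reading of one exploratory contrast. It is, however, the plan's only comparison with women outside the intervention. The pre-post comparison cannot separate the intervention from recovery after surgery.

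**Working it through.** **Is there a stated figure to reproduce?** No. The sample size of 30 is set on feasibility, and no alpha, power, SD or effect size attaches to this contrast. What follows illustrates scale and is not an estimate of bias in this study.

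**Inputs from the documents**
- 30 pilot women and 60 cohort women.
- Repair success 50% to 90% by severity (Background and Justification).
- Reintegration gap for persistent symptoms at twelve months: 21.9 points, 95% CI 13.5 to 30.2 in absolute value (Study Goals and Objectives).

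**Assumptions**
- Failed repair is equated with persistent symptoms.
- The twelve-month gap holds at six months.
- SD is 18, and the test is two-sided at 5%.

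**Basis for SD 18.** The printed 32.8%, 17.2% and 8.6% fit 19, 10 and 5 women out of 58, and no other denominator from 40 to 60 reproduces all three. The CI of the gap gives SE = (30.2 - 13.5)/3.92 = 4.26. With 19 to 34 of 58 women symptomatic, the within-group SD is about 15 to 16. Adding the between-group part, f(1 - f) x 21.9², gives a total SD of about 18 to 19.5. This presumes the CI is unadjusted, which is not stated.

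**Precision of the crude contrast.** SE = 18 x sqrt(1/30 + 1/60) = 4.02. Half-width = t(0.975, 88 df) x SE = 1.987 x 4.02 = 8.0 points.

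**Effect of a case-mix shift.** Symptom difference = shift between the extreme severity strata x (0.90 - 0.50). Shift in the contrast = symptom difference x 21.9. Rejection under no intervention effect comes from the noncentral t with 88 df.

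| Severity shift | Symptom difference | Contrast shift (range over CI of gap) | Share of half-width | Rejection, SD 18 (range over CI of gap) | Rejection, SD 22 to SD 15 | Rejection, 27 vs 54 women |
|---|---|---|---|---|---|---|
| 10 points | 4 points | 0.9 (0.5-1.2) | 11% | 5.5% (5.2%-6.0%) | 5.4%-5.8% | 5.5% |
| 25 points | 10 points | 2.2 (1.4-3.0) | 27% | 8.4% (6.3%-11.5%) | 7.2%-9.9% | 8.0% |
| 50 points | 20 points | 4.4 (2.7-6.0) | 55% | 19.0% (10.2%-31.7%) | 14.2%-25.3% | 17.5% |

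The last row is an extreme case. The mapping is rough throughout, because persistent symptoms also include weakness and pain, which no section ties to severity.

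**What adjustment does.** A simulation (4,000 runs, 30 vs 60 women, within-group SD 15.2, no intervention effect) used a prognostic factor worth 21.9 points, measured alike in both series. With prevalence 13% in the pilot and 33% in the cohort, the crude difference averaged 4.4 points with 17% rejection. Adjusted for the factor, the difference averaged about zero with 5% rejection. This shows the principle only for a factor recorded in both datasets.

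**Precision cost.** Three covariates that explain nothing reduce 88 df to 85, and the half-width goes from 7.999 to 8.003 points. If the covariates explain 10% of group membership, the half-width grows by sqrt(1/(1 - 0.10)) = 1.054, about 5%.

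**The case against.** The strongest reply is that nothing here demonstrates bias. No section gives a case-mix difference, the modest scenario lifts rejection only from 5.0% to 5.5%, and the plan states no alpha. The 21.9-point gap concerns a post-operative state at twelve months, so its link to baseline severity is indirect. SD 18 is the low end of the derived range; at 19.5 the 25-point scenario gives 7.9% instead of 8.4%. All of this stands, and it is why the point is minor.

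The plan also intends to recruit every eligible woman who presents, which limits selection into the pilot. The summary says no comparison group is included at this stage, and the within-woman comparison is unaffected by differences between the series. These points are fair, but none shows whether the 2020-2021 women resemble those of 2015-2016. Publications on the cohort are cited and may report its baseline; that cannot be judged from the documents.

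Feasibility of adjustment is the most practical objection. The cohort's baseline variables are not listed. The Study Participants section also makes women eligible after surgery, whereas the Recruitment and Enrollment section and the intervention timeline place recruitment and first sessions before it, so some baselines could be post-operative. Adjustment must therefore be restricted to confirmed pre-surgical variables. Finally, an adjusted estimate can look more credible than it is, which is a reason to show it beside the crude one with its limits stated.

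**Conclusion.** The concern holds, as a minor one. The absence of any balance check or adjustment is certain from the text. The consequence is not: the size and direction of any bias are unknown, and the scenario figures depend on the assumed SD, the assumed 5% test, carrying the twelve-month gap to six months, and equating failed repair with persistent symptoms. Moderate case-mix shifts would move the contrast by a small part of its confidence interval; only an extreme shift would move it by about half of the half-width.

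No decision rule rests on this contrast, and no section says it will set the effect size of the later trial. As planned, though, the analysis gives no means of judging whether a difference, or its absence, reflects the women enrolled. Adjustment would address only case mix measured in both datasets.

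**What to change.** 1. Tabulate pilot and cohort baseline characteristics side by side.
2. Prespecify an adjusted estimate, reported beside the crude one, each with a 95% CI: a linear model of the six-month outcome on study group, logistic for binary outcomes. Adjust for the pre-surgical baseline score on the same scale where both datasets hold it, and for one or two pre-surgical variables confirmed in both, such as fistula severity or type and duration with fistula. If the cohort lacks a baseline score on a scale, use the clinical variables alone and say so.
3. Do not adjust for post-operative symptoms, which the intervention may change.
4. State that calendar-time, site and unmeasured differences remain and that the contrast is not causal.

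The cost is a few sentences of plan, a check of which variables the cohort dataset holds, and a little analysis. The pilot already collects baseline reintegration status, fistula characteristics and time with fistula. The downside is two or three degrees of freedom from at most 90 women, plus some loss of precision if the groups are imbalanced. Logistic models may support only one covariate if events are few.

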Appendix 1A. Overview of Reintegration Intervention: Health Education Sessions

Session	Objective	Length	Timing ^a	Delivery ¹
1. Admission and Preoperative Management: Preparing for Upcoming Surgery and Recovery (Part 1)	
 Introduce patients to fistula Introduce patients to care providers Provide a comprehensive overview of procedure, risks, and outcomes Address any patient concerns and questions about procedure and recovery 	30m	Pre-op Day 1	Group
2. Admission and Preoperative Management: Preparing for Upcoming Surgery and Recovery (Part 2)	
 Familiarize patients to the patient ward and the surgical theatre Discuss preoperative preparations Discuss postoperative management Address any patient concerns and questions about procedure and recovery 	30m	Pre-op Day 2	Group
Surgery Day 0				
Post-op Day 1				
3. Overview of Postoperative Management	
 To discuss outcomes of surgery To discuss postoperative care management at the facility Address any patient concerns and questions 	30m	Day 2 (post-op)	Group
4. Reproductive system anatomy and function	
 Familiarize participants with the female reproductive system and female pelvis, anatomy and functions 	30m	Day 2 (post-op)	Group
5. Development of Fistula	
 Identify the causes of obstetric fistula 	30m	Day 4 (post-op)	Group
6. Common Myths and Misconceptions about Fistula	
 To dispel any common rumors and myths about obstetric fistula To explaining how these may hamper women's ability to prevent fistula and to access treatment 	30m	Day 4 (post-op)	Group
7. Health and Social Consequences of Fistula	
 To identify and discuss the health consequences of fistula To identify and discuss the social consequences of fistula 	20m	Day 6 (post-op)	Group
8. Fistula Prevention	
 To discuss ways to prevent obstetric fistula after repair To introduce birth spacing 	40m	Day 6 (post-op)	Group

¹ Where group is indicated but women are in undergoing fistula repair without other fistula patients concurrently on the ward, they will receive a modified version of the activity appropriate for delivery to the individual.

9. Sexual and Reproductive Health after Fistula	
 • To educate patients on sexual health • To familiarize participants reproductive tract issues • To identify personal timelines for family planning and fertility preferences 	30m	Day 8 (post-op)	Group
10. Family Planning	
 • To identify different family planning methods • To dispel myths and misconceptions regarding contraceptives • To facilitate discussion of which family planning method might be right for the participant 	30m	Day 8 (post-op)	Group
11. Future Obstetric Care	
 • To understand the components and reasons for antenatal care during pregnancy • To recognize the danger signs during pregnancy • To discuss the importance of planning and preparation for safe delivery • Facilitate participant creation of birth plan 	30m	Day 10 (post-op)	Group
12. Nutrition	
 • To understand optimizing nutrition for recovery 	30m	Day 10 (post-op)	Group
13. Post-discharge management	
 • To identify ways on how to take care of herself at home • To discuss the importance of follow-up visits • To recognize surgical warning after discharge • Facilitate participants in creating a complication 	30m	Day 12 (post-op)	Group
14. Recap of Health Education Sessions	
 • To prepare the patient for her return home, which maximizes the likelihood of a positive reintegration experience. • To review all of the materials and information discussed during the health education sessions • For participants to share their experiences, ask questions 	30m	Day 12, 13, or 14 (post-op)	Group
15. Health Education Counseling for the Participant's Family &/ Caretaker (optional)	
 • To communicate patient's health condition and treatment (only if requested to be shared with family member(s) &/or caretaker • To communicate any risks and possible side effects • To address any concerns and questions brought up by patient's social support • To identify warning signs • To develop plan in case of complications 	60m	TBD	Group

	
 • To provide guidance on how to support patient at home • To discuss sexuality after surgical repair • To discuss reproductive tract and sexually transmitted infections 			
--	--	--	--	--

Appendix 1B. Overview of Reintegration Intervention: Psychological Counseling Sessions

Session	Objective	Length	Timing ^a	Delivery ²
1. Introduction to Psychological Counseling	
 • Introduction to counseling • Assessing the patient's needs and concerns • Set Initial Treatment Plan/Goals • Facility nurse will determine if patient is ready for group counseling session. 	40m	Pre-op	Individual
Surgery Day 0				
Post-op Day 1				
2. Exploring the Fistula Experience	
 • To get familiar to each other • To normalize the patient's experience • To acknowledge the negative and possible positive impacts of the fistula experience on relationships with others • To begin exploration of how the patient's experience of an obstetric fistula impacts her feelings and thoughts about herself 	60m	Day 3 (post-op)	Group
3. Cognitive reframing the Fistula Experience	
 • To promote cognitive reframing of the fistula experience through medical education • Help the patient reframe her personal narrative 	60m	Day 5 (post-op)	Group
4. Identifying Thoughts and Emotions	
 • To introduce the patient to the cognitive-behavioral model • To begin teaching patient how to reframe negative or unhelpful thoughts • Review key emotions • Identify negative and problematic thoughts • Link thoughts to resulting emotions 	60m	Day 7 (post-op)	Group

² Where group is indicated but women are in undergoing fistula repair without other fistula patients concurrently on the ward, they will receive a modified version of the activity appropriate for delivery to the individual.

	
 • Begin practicing reframing problematic thoughts • To manage the emotions associated with their situation 			
5. Develop Coping Strategies	
 • To help the patient to recognize and respond to stressors in her life by utilizing appropriate and effective coping skills. • Discuss the patient's negative vs. positive coping strategies • Coach patient to recognize stressors and respond by utilizing appropriate and effective coping skills. 	40m	Day 9 (post-op)	Group
6. Explore Social Relationships	
 • To examine the effect of social relationships on the patient's life • To generate specific strategies to strengthen social relationships • Discuss how one's social network influences thoughts and feelings • Formulate strategies to expand and optimize patient's social support network • Review tools to discuss her condition with others • To practice communication skills. • Mobilize home support by identifying partner &/ caregiver to participate in optional combined counseling session 	20m	Day 10 (post-op)	Group
7. Planning for the Future	
 • To prepare the patient for her return home, which maximizes the likelihood of a positive reintegration experience. • Make practical plans for the patient's return to her community • Discuss the possibility of incomplete cure & post-surgery medical recommendations 	60m	Day 11 (post-op)	Group
8. Patient Pre-discharge Assessment	
 • Review therapy action plan and discuss progress in reaching goals • Patient assessment and addressing patient's remaining needs and concerns • Identify if patient requires additional psychiatric counseling/emotional support/medication if patient suffers from trauma-related fistula 	60 minutes	Day 13 or 4 (post-op)	Individual

9. Building Social Support Opportunities (OPTIONAL)	
 Intended to facilitate social support for patient returning home after repair 	60m	Offered between days 10-15 (post-op)	Group (with patient and partner & caretaker)
--	---	-----	--------------------------------------	--

